### 1.2.1.2.4 Clinical pharmacokinetics

In adult patients with tumors characterized by genetic abnormalities in ALK [REDACTED] and in healthy volunteers [REDACTED] and [REDACTED] the single-dose pharmacokinetics of LDK378 in humans has the following features: (1) LDK378 was slowly absorbed, with median peak plasma concentration occurring at approximately 4 to 6 h in patients, and approximately 6 to 8 h in healthy subjects. Following Cmax, LDK378 concentrations declined in a mono-exponential manner. The geometric mean apparent terminal half-life ranged from 31 to 41 h across the 400 to 750 mg dose groups in patients and 36 to 48 h across the 450 to 750 mg dose groups in healthy subjects. (2) Cmax and AUClast increased dose-proportionally following single oral administration of LDK378 across the 50 to 750 mg dose groups. (3) Moderate to high variability in LDK378 PK parameters has been observed in both healthy subjects and patients. Following single oral doses of 450 to 750 mg in healthy subjects when LDK378 was given alone, the inter-subject variability (geometric mean coefficient of variation; CV% range) was 42-74% and 35-72% for AUClast and Cmax, respectively. The corresponding values in patients were 93% and 87% following single oral doses of 50 to 750 mg based on a model developed for dose proportionality analysis.

[REDACTED]

The multiple-dose PK of LDK378 following repeated daily oral dosing in patients has the following features: (1) AUCtau at the maximum tolerated dose and recommended dose of 750 mg increased from first dose with geometric mean accumulation ratios of 4.7 on Cycle 1 Day 8 after 1 week of daily dosing and 6.2 on Cycle 2 Day 1 after 3 weeks of daily dosing, respectively. Evaluation of trough concentration at 750 mg that steady-state was achieved by Cycle 1 Day 15 following 2 weeks of daily dosing. (2) LDK378 demonstrated nonlinear PK over time, as indicated by the observed difference in apparent clearance (CL/F) between single-dose (88.5 L/h at 750 mg) and steady-state at Cycle 2 Day 1 (33.2 L/h at 750 mg). As LDK378 is a substrate as well as a time-dependent inhibitor of CYP3A, it is likely that this PK nonlinearity could be attributed to auto inhibition of LDK378. In contrast with single dose data, Ctrough on Cycle 2 Day 1 after repeated daily dosing increased with dose in a greater than dose-proportional manner.

[REDACTED]

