A patient is considered to have met the minimum exposure criterion if s/he received at least 16 out of the 21 planned once daily doses of LDK378 in the first 21 days of dosing. Patients who do not experience DLT during the first cycle are considered to have sufficient safety evaluations if they have been observed for at least 21 days following the first dose, and are considered by both the Sponsor and Investigators to have sufficient safety data to conclude that a DLT did not occur.

Patients who do not meet these minimum safety evaluation requirements and who did not discontinue earlier due to a DLT will be regarded as ineligible for the DDS.

Pharmacokinetic analysis set

The pharmacokinetic analysis set (PAS) consists of all patients who received at least one dose of LDK378 and have at least one evaluable pharmacokinetic (PK) sample.

Depending on whether the sample is part of a full profile or a trough collection, the specific criteria are listed as follows.

An evaluable full PK profile is defined as:

1. On the PK collection day, no vomiting occurred within 4 hours of dosing on the full PK sampling day (i.e., no vomiting within 4 hours after Cycle 1 Day 1 dose or after Cycle 2 Day 1 dose), AND
2. On the PK collection day, the patient takes study drug according to the originally assigned dose, AND
3. The patient takes study drug according to the originally assigned dose for at least 5 consecutive days without interruption or dose modification prior to the PK sampling day (except for Cycle 1 Day 1, i.e., only applicable to Cycle 2 Day 1), AND

4. On the PK collection day, the patient takes study drug under the originally assigned prandial condition, AND
5. The patient takes study drug under the originally assigned prandial conditions, i.e., dose administered without food for patients in the fasted cohort, or dose administered with light snack food for patients in the fed cohort, for at least 5 consecutive days prior to the PK sampling day (except for Cycle 1 Day 1, i.e., only applicable to Cycle 2 Day 1), AND Additionally, an entire profile can be considered non-evaluable as per scientific judgment of the clinical pharmacology expert even if the above criteria are fulfilled. Reason will be documented.

An evaluable trough PK concentration (C_{min}) is defined as:

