1. the patient takes study drug according to the originally assigned dose for at least 5 consecutive days prior to the PK sampling day (except for Cycle 1 Day 1 in dose escalation and expansion phases), AND no vomiting occurs within 4 hours following the last dose intake prior to the PK sample draw,
2. For the pre-dose or 24 hour post-dose sample, draw must occur between 0 to 6 hours before the dose that is immediately after, AND
3. The patient takes study drug under the originally assigned prandial conditions, i.e., dose administered without food for patients in the fasted cohort, or dose administered with light snack food for patients in the fed cohort, for at least 5 consecutive days prior to the PK sampling day (except for Cycle 1 Day 1), AND Additionally, a sample can be considered non-evaluable as per scientific judgment of the clinical pharmacology expert even if the above criteria are fulfilled. Reason will be documented.

A patient belongs to PAS if he/she has either an evaluable full PK profile or an evaluable trough PK sample.

Any blood samples missing blood collection date or time, or missing associated study drug dosing date or time will be excluded.

Frequency counts and percentages (using FAS as denominator) of patients in each of the above defined analysis sets will be summarized. In addition, listings of patients included in each of the analysis sets will be provided.

Section 2.3.5 provides further details regarding the derivation of the analysis sets.

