Concentration values below the lower limit of quantitation (LLOQ) (< 1.0 ng/mL) will be displayed in listings as zero with a flag and handled as zero in the calculations of summary statistics except for geometric means and associated CVs where they will be set to missing. Any missing PK parameters will not be imputed.

LDK378 concentrations

Summary statistics, including n, mean, SD, coefficient of variation CV (%) for mean, geometric mean, geometric CV (%), median, minimum and maximum, will be presented for evaluable PK plasma concentration of LDK378 following the general reporting rule for PK, by treatment and scheduled time point for both full PK profile and trough PK concentrations, separately for fasted and fed patients and for escalation phase and expansion phase. For patients with full PK profile on Cycle 1 Day 1 or Cycle 2 Day 1, corresponding graphical presentations of the plasma concentration profiles will be provided by treatment using arithmetic mean (+/- SD) and geometric mean values at each scheduled time point. The individual plot will also be provided.

LDK378 PK parameters

Primary and secondary PK parameters will be summarized using the same reporting approach as for LDK378 concentrations, by treatment, separately for Cycle 1 Day 1 and Cycle 2 Day 1 for fasted and fed patients in the escalation and expansion phase. For Tmax, only median, minimum and maximum will be presented.

All PK parameters and concentration data will be listed by treatment using PAS.

Dose proportionality (DP) analysis

DP analysis at single dose (Cycle 1 Day 1) and steady state (Cycle 2 Day 1): Data from both dose-escalation phase and expansion phase will be used. AUC0-24h and Cmax will be analyzed. All dose levels will be included.

DP will be assessed via the following model as well as graphical presentations.

DP is analyzed by fitting a linear model as described below.

$$\ln(\text{PK}) = \alpha + \beta * \ln(\text{actual dose}),$$

where PK is the PK parameter, AUC₀₋₂₄ or C_{max}, and actual dose (mg/m²) is defined as dose divided by BSA.

The estimate and its 90% confidence interval (CIs) for β in each case are reported. As an informal comparison, the estimates and CIs for β are compared to the target dose-proportionality range, calculated by the following formula (Smith, 2000).

Lower bound of target dose-proportionality range of β : $1 + \ln(0.8)/\ln(\text{dose range})$

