- The patient takes study drug under the originally assigned prandial conditions, i.e., dose

administered without food for patients randomized to the treatment arm of 750 mg fasted, or dose administered with food for patients randomized to the treatment arm of 450 mg with low-fat meal or 600 mg with low-fat meal, for at least 5 consecutive days prior to the PK sampling day (except for Cycle 1 Day 1)

This allows exposure-response analyses to take into account the exposure after study drug interruption, dose reduction, vomiting or fail to adhere to the assigned prandial condition for individual patient.

Quartile ranges of C_{trough_avg} are defined as:

- <Q1: <25th percentile
- Q1-<Q2: ≥25th percentile and <50th percentile
- Q2-<Q3: ≥50th percentile and <75th percentile
- ≥Q3: ≥75th percentile

C_{trough_avg} and its quartile values will be used in display of AE.

Inter and intra patient variation

The intra-patient and inter-patient variations will be evaluated using data from patients at MTD with one or more than one evaluable steady state trough PK measurements. Evaluable trough concentration is defined in PAS. For steady state trough concentration, we will only consider trough values collected on or after C1D15 (C1D1 sample will not be used in the analysis). The intra-patient and inter-patient variations will be estimated using random effects model with treatment as a fixed effect and patient as a random effect. See [Section 5.7](#) for more details.

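### Cycle 2 Day 1 profiles and later troughs count as steady state after 5 days at the assigned dose, although the protocol puts steady state at 2 weeks; recently interrupted patients should be flagged.

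*SAP*

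**What the plan says.** SAP 2.2 defines an evaluable full PK profile. For C2D1, the patient must have taken the originally assigned dose "for at least 5 consecutive days without interruption or dose modification prior to the PK sampling day", and must have kept to the assigned prandial condition over the same period. For an evaluable trough, SAP 2.2 asks for the assigned dose "for at least 5 consecutive days prior to the PK sampling day". Both definitions also allow exclusion by judgment: "an entire profile can be considered non-evaluable as per scientific judgment of the clinical pharmacology expert even if the above criteria are fulfilled", with the reason documented.

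SAP 2.10 then treats these records as steady state. The steady-state dose-proportionality model uses C2D1. Racc and CLss/F are defined on steady-state exposure. For inter- and intra-patient variation, the SAP says: "For steady state trough concentration, we will only consider trough values collected on or after C1D15". That is a calendar cut-off. It does not require uninterrupted dosing up to that day.

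Protocol 1.2.1.2.4 describes adults on 750 mg daily. It reports that "steady-state was achieved by Cycle 1 Day 15 following 2 weeks of daily dosing" and gives "geometric mean accumulation ratios of 4.7 on Cycle 1 Day 8 after 1 week of daily dosing and 6.2 on Cycle 2 Day 1".

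**The concern.** Five days is a plausible run-in if one thinks of the single-dose half-life: "The geometric mean apparent terminal half-life ranged from 31 to 41 h". On repeated dosing, though, the protocol reports apparent clearance falling from 88.5 to 33.2 L/h and accumulation still rising after the first week. A patient held in Cycle 1 and restarted at the assigned dose on Day 17 meets the rule on Day 22 while still re-accumulating. The rule takes no account of how long the hold was.

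The error runs in one direction: AUCtau, Racc and T1/2,acc too low, CLss/F too high. The rule also appears intended to prevent exactly this. SAP 2.10 drops it for the average trough so that the exposure-response analysis can reflect exposure after interruptions, which implies that the other summaries are meant to be free of them.

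Such patients are foreseeable. Protocol Table 6-4 has holds followed by the same dose level, for example a first Grade 2 diarrhea or vomiting, or Grade 2 creatinine resolving within 7 days.

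**Working it through.** **Without a model.** 4.7/6.2 = 0.758. A full week of dosing from zero gives 76% of the C2D1 accumulation.

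**Inputs.** Accumulation ratios 4.7 (C1D8) and 6.2 (C2D1), steady state by C1D15, and single-dose half-life 31 to 41 h come from protocol 1.2.1.2.4. Protocol 6.4.2.7 equates 9 days with five half-lives, so 9 × 24/5 = 43.2 h. The 5-day run-in comes from SAP 2.2. Two assumptions are mine: linear superposition with a 24 h interval, and carry-over of adult data to children.

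**Effective half-life.** With r the fraction remaining after 24 h, Racc = 1/(1 − r). So r = 1 − 1/6.2 = 0.8387, and the half-life is 24 × ln 2 / ln(6.2/5.2) = 94.6 h. A rough second route is 36 h (protocol 2.3) × 88.5/33.2 = 96 h, if the volume of distribution is unchanged.

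**Reproducing the protocol's figures.** R(n) = (1 − r^n)/(1 − r) gives R(8) = 4.68 against the stated 4.7. R(15)/R(22) = 0.948, consistent with steady state by Day 15. A 36 h half-life would give Racc = 2.7, not 6.2, so the single-dose half-life does not describe repeated dosing.

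**Effect of a gap.** Exposure on Day 22 relative to no gap = 1 − (sum of r^(22−d) over missed days d) / (sum of r^j, j = 0 to 21). The denominator is 6.071.

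- One dose missed on Day 16, Days 17 to 21 taken: 1 − 0.348/6.071 = 0.943.
- Five doses missed on Days 12 to 16: 1 − 1.262/6.071 = 0.792. Then CLss/F is 1/0.792 = 1.26 times the uninterrupted value and Racc is 6.2 × 0.792 = 4.91. T1/2,acc becomes 24 × ln 2 / ln(4.91/3.91) = 73 h instead of 94.6 h.

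| Missed doses | Gap ends Day 16, 94.6 h | CLss/F too high by | Mean over gap positions, 94.6 h | Gap ends Day 16, 43.2 h |
|---|---|---|---|---|
| 1 | 94.3% | 6% | 98% | 96.8% |
| 3 | 85.4% | 17% | 94% | 93.2% |
| 5 | 79.2% | 26% | 90% | 91.5% |

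The mean column averages over gaps ending on any day up to Day 16, with at least one dose taken first. At 31 h the Day 16 figures are 98.3%, 96.8% and 96.3%.

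**With 14 uninterrupted days before C2D1.** Exposure at 94.6 h is 98.8% (1 missed dose) to 95.2% (6 missed, the longest gap that fits after a first dose). At 43.2 h or shorter it is at least 99.7%.

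**The case against.** The case for leaving the rule alone has real substance.

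- **Expert exclusion.** SAP 2.2 lets the clinical pharmacology expert remove a profile that meets the criteria. This may catch some restarted patients, but it is discretionary and sets no steady-state criterion. It softens the problem without removing it.
- **Few patients may be affected.** A reduced dose cannot be re-escalated (protocol 6.3.1), so dose-reduced patients already fail the assigned-dose criteria. Only same-dose restarts get through. This stands.
- **Long holds are mostly screened out.** A reader might take a week-long hold as the typical case, giving 74.8% of exposure at 94.6 h. Seven missed doses leave 14 of 21. If the cause is toxicity at least possibly related to the drug, delivering fewer than 16 doses is itself a DLT, and protocol 6.2.4 generally has such patients resume lower. Exceptions exist, but five missed doses is a fairer upper case.
- **Worst placement and borrowed data.** The larger figures put the gap directly before the run-in and apply a linear model to adult data for a drug with time-dependent clearance. That is why the mean over positions and the 43 h case are shown.
- **Descriptive use.** Dose proportionality is an informal, unpowered comparison in SAP 2.10. Single-dose between-subject CVs in patients were 93% and 87%, so a shift in a few profiles may be hard to see in a group mean.

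Two further inferences are not supported. One is that the rule distorts the choice between fasted and fed dosing: the SAP summarises the regimens separately and specifies no PK comparison, and the fed regimen had been chosen by Amendment 6, before this SAP, which is based on Amendment 8. The other is that the dose-proportionality slope is flattened. That needs same-dose restarts to cluster at higher doses, which the documents do not show.

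**Conclusion.** The concern holds, within limits. The SAP labels as steady state some records that the protocol's own data say may not have reached it, and the resulting bias has a known direction. It affects only patients interrupted in Cycle 1 who resumed at the assigned dose: AUCtau and CLss/F in both parts of the study, and Racc only in escalation, where a Day 1 profile exists.

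For such a patient, exposure is about 6% to 21% low for 1 to 5 missed doses in the worst position at 94.6 h, 2% to 10% low on average over positions, and about 3% to 9% low in the worst position at 43 h. These sizes rest on linear superposition and on adult 750 mg data. The effect on any summary table cannot be stated, because the documents do not give the frequency of qualifying interruptions. This is a weakness in secondary, descriptive PK results and does not touch the MTD/RDE.

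**What to change.** In SAP 2.2 and 2.10, derive from the dosing records a flag for any C2D1 profile or steady-state trough with a missed or modified dose in the 14 days before sampling. Report the steady-state AUCtau, Cmax, CLss/F, Racc, dose-proportionality and trough inter-/intra-patient CV results with and without flagged records, and give the number flagged. T1/2,acc, which SAP 2.10 only lists, should carry the same flag and be shown both ways if it is summarised. Keep flagged records in the PAS and listings.

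A strict 14-day exclusion as the main rule is not advised. One missed dose on Day 8 changes C2D1 exposure by only 1.4% at 94.6 h (0.8387^14/6.071 = 0.014), yet it would drop the profile from cohorts of 3 to 6.

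The cost is one extra derivation from existing data and a second set of summaries. That second set has fewer profiles and over-represents patients who tolerated the drug well, so it should be read alongside the full set and not in place of it.

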2.3 Patient disposition, demographics and other baseline characteristics

The FAS will be used for all patient demographic and baseline characteristic summaries and listings, unless otherwise specified.

Basic demographic and background data

All demographic and baseline disease characteristics data will be summarized and listed for all patients. Categorical data (e.g. gender; age groups: 1 year to <7 years, 7 years to <12 years, 12 years to <18 years; race; ethnicity; Karnofsky or Lansky performance status) will be summarized by frequency count and percentages. Continuous data (i.e. age, weight, height, body surface area) will be summarized by descriptive statistics (as defined in [Section 2.1](#)).

All data collected during the baseline evaluation will be listed.

Diagnosis and extent of cancer

Descriptive statistics and frequency counts and percentages will be tabulated, as appropriate, for diagnosis and extent of cancer based on the data collected on the eCRF including primary site of cancer, time (in months) from initial diagnosis of primary site to start date of study drug, time (in months) since most recent recurrence/relapse or progression to start date of study drug, current extent of disease (metastatic sites), types of lesions (target and non-target lesions) at baseline, and disease burden at baseline for target lesion. Note: Presence/absence of target and non-target lesions will be based on the data collected on RECIST target/non-target lesion assessment eCRF pages. Presence/absence of index and non-index lesions will be based on the data collected on Lymphoma index/non-index lesion assessment eCRF pages. Metastatic sites will be based on diagnosis page.

ALK status

If ALK status is not already known, patients will be tested for ALK positive status using a Novartis designated central laboratory. ALK status from local and central laboratory results at baseline as determined in the retrospective collection of pathological reports will be summarized using frequency counts and percentages for patients. The ALK status summary includes test result (positive, negative, not evaluable), ALK abnormality type (ALK translocation, ALK amplification, ALK point mutation, other), test methodology used (FISH, IHC, RT-PCR, sequencing DNA/RNA, other).

All other ALK data collected during the baseline evaluation will be listed.

Medical history

Medical history and current medical conditions, including cancer-related conditions and symptoms will be summarized and listed. Separate summaries will be presented for ongoing and historical medical conditions. The summaries will be presented by primary system organ class (SOC) and preferred term (PT). Medical history and current medical conditions are coded using the Medical Dictionary for Regulatory Activities (MedDRA) terminology.

Protocol deviations

Frequency counts and percentages of patients in the FAS with any protocol deviations (inclusion/exclusion criteria not met, patient not withdrawn as per protocol, key procedures not performed as per protocol, treatment deviation, prohibited concomitant medication, Good Clinical Practice (GCP) deviation) will be tabulated by the deviation category. The full list of protocol deviations are documented in the Data Handling Plan (DHP). All protocol deviations will be listed.

Prior antineoplastic therapy

Prior anti-neoplastic (anti-cancer) therapy will be listed in three separate categories: (i) medications, (ii) radiotherapy, and (iii) surgery.

The number and percentage of patients who received any prior anti-neoplastic medications, prior anti-neoplastic radiotherapy or prior anti-neoplastic surgery will be summarized.

The summary of prior anti-neoplastic medications will include the total number of regimen, setting at last medication, the time between end of last medication to start of treatment in days (end of last medication is based on end date of last dose, the best response at last medication (defined to be the best response during the last treatment regimen recorded), and time (in months) from start of last medication to progression. The last medication is defined taking into account the end date. Prior antineoplastic medications will also be summarized by ATC class, and preferred term.

The summary of prior anti-neoplastic radiotherapy will include a summary of radiotherapy locations, including all locations recorded for each patient. Setting, method, and best response at last radiotherapy will also be summarized.

The summary of prior anti-neoplastic surgery (excluding diagnostic biopsies) will include the time between the last surgery to start of treatment, procedure at last surgery and residual disease at last surgery.

2.3.1 Patient disposition

Screen failures

Screen failures will comprise patients who have been enrolled and signed study ICF, and screened to the study and have failed to meet inclusion or exclusion criteria. These patients are not treated with study drug. Frequency counts and percentages will be tabulated for all enrolled patients as follows:

- Number (%) of patients who completed screening phase (based on the presence of 'Screening log' and 'Demography' page);
- Number (%) of patients who discontinued during screening phase (based on the presence of discontinuation reason entered and 'Will the subject enter the study' is 'No' in the 'Screening log' page) ;
- Reasons for screening phase discontinuation (based on reasons recorded in Screening log' page).

All screen failure patients with reasons for screen failure will be listed.

Patient Disposition

The FAS will be used for the patient disposition summary tables and listings. The following will be tabulated:

- Number (%) of patients who are still ongoing-treatment (based on the absence of the 'End of Treatment' page);
- Number (%) of patients who discontinued treatment (based on completion of the 'End of Treatment' page with date of discontinuation and reason of discontinuation entered);
- Primary reasons for study treatment discontinuation (based on discontinuation reasons entered in the 'End of Treatment' page);
- Number (%) of patients who discontinued from study (based on completion of 'Study evaluation completion' page);

- Number (%) of patients who discontinued treatment but continued to be followed (based on completion of 'End of Treatment' page and 'Study evaluation completion' page not completed);
- Primary reasons for study evaluation completion (based on primary reason for study evaluation completion in the 'Study evaluation completion' page).

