#### **7.1.1.2 Information to be collected on screening failures**

Patients who sign the molecular pre-screening ICF but do not meet the pre-screening requirements will be considered a screen failure. The reason will be entered on the Screening Log eCRF, and each patient's demographic information will be added to the Demography eCRF. No other data will be entered into the clinical database for patients who are screen failures.

Patients who meet molecular pre-screening requirements and sign the main ICF but do not start treatment for any reason will be considered a screen failure. The reason for not being started on treatment will be entered on the Screening Log eCRF, and each patient's demographic information will be added to the Demography eCRF. No other data will be entered into the clinical database for patients who are screen failures.

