2.2 Analysis sets

A patient is considered to be enrolled into the study if they have signed study informed consent. Only patients who have signed study informed consent prior to study procedures will be included in the analysis data sets.

Full analysis set

The Full Analysis Set (FAS) includes all patients who received at least one dose of LDK378. Patients will be classified according to the intended/planned treatment. The FAS will be used for all listings of raw data. Unless otherwise specified, the FAS will be the default analysis set used for all analyses.

The planned treatment will be based on the first dosing record. The corresponding fasted/fed status will be determined as per [Table 2-1](#) below as per protocol.

Table 2-1 Dose level and fasted/fed status

Dose Levels	Fasted/Fed Status
200 mg/m ²	Fasted
300 mg/m ²	Fasted
450 mg/m ²	Fasted
510 mg/m ²	Fasted
560 mg/m ²	Fasted
320 mg/m ²	Fed
400 mg/m ²	Fed
500 mg/m ²	Fed

Safety set

The safety set includes all patients who received at least one dose of LDK378.

The patients will be classified according to treatment received, where treatment received is defined as:

1. The actual dose level (mg/m^2) is the planned dose level if any actual total daily dose administered is equal to the value of “the planned dose levels ([Table 2-1](#)) * BSA (m^2) rounds to the nearest 50 mg”. For 25/75 mg, either rounding up or rounding down is acceptable.
2. The first actual dose level in the study (converts actual total daily dose administered / BSA (m^2) and maps to nearest planned dose levels) if the planned dose level was never received.

BSA = The last available BSA measurement on or before dosing date will be used in the calculation for actual dose level.

For example, if a patient from 500 mg/m^2 fed group doesn't meet the first criteria, and the first actual dose level in the study is 150 mg. Suppose this patient has BSA=0.45 m^2 on/before the first dose, then the first actual dose level in the study=actual total daily dose administered / BSA (m^2)=333 mg/m^2 , which will be rounded to the nearest planned dose level 320 mg/m^2 fed.

Dose determining set

The dose determining analysis set (DDS) consists of all patients from the safety set who *either* meet the minimum exposure criterion and have sufficient safety evaluations *or* discontinue earlier due to DLT in the escalation phase.

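### SAP 2.3.1 identifies screening completers by two eCRF pages that the protocol also fills for every screen failure, so main-consent failures are counted as both completed and discontinued

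*SAP*

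**What the plan says.** The screen-failure part of SAP 2.3.1 sets the denominator: "Frequency counts and percentages will be tabulated for all enrolled patients as follows". SAP 2.2 defines enrolment: "A patient is considered to be enrolled into the study if they have signed study informed consent".

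Two rows matter here.

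- Completed: "Number (%) of patients who completed screening phase (based on the presence of 'Screening log' and 'Demography' page". No condition is placed on what either page says.
- Discontinued: "Number (%) of patients who discontinued during screening phase", which is "based on the presence of discontinuation reason entered and 'Will the subject enter the study' is 'No' in the 'Screening log' page". This rule does depend on page content.

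The same part of SAP 2.3.1 also calls for a tabulation of reasons and a listing of all screen failures with their reasons.

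Protocol 7.1.1.2 recognises two kinds of screen failure. The first: "Patients who sign the molecular pre-screening ICF but do not meet the pre-screening requirements will be considered a screen failure". The second covers those who pass molecular pre-screening and "sign the main ICF but do not start treatment for any reason will be considered a screen failure". Both kinds get a Screening Log entry and a Demography entry. For the second kind the text reads "The reason for not being started on treatment will be entered on the Screening Log eCRF, and each patient's demographic information" and goes on to place those demographics on the Demography eCRF. Nothing else is entered in the database for a screen failure.

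**The concern.** The two pages that define a completer are exactly the two pages that every screen failure has. A rule based on their presence therefore cannot tell the groups apart. Completed and discontinued are plainly meant as alternatives, yet the same patient can fall in both.

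Elsewhere in SAP 2.3.1 the page rules do separate patients: an absent End of Treatment page marks ongoing treatment and a completed one marks discontinuation. The completed-screening row is the one that lacks a discriminator.

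What is at stake is one reported count and percentage. The introduction to SAP Section 2 says that the section will be carried into the methods part of the clinical study report, so the faulty definition would go with it.

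**Working it through.** The plan states no figure on this point, so there is nothing to reproduce. The check applies the two SAP rules to the pages that the protocol requires.

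**Step 1: which rule each patient meets**

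| Patient | Screening Log page | Demography page | Meets completed rule | Meets discontinued rule |
|---|---|---|---|---|
| Treated | yes (assumed) | yes | yes | no |
| Signed main consent, marked 'No' with a reason | yes | yes | yes | yes |
| Signed main consent, marked 'No', reason missing | yes | yes | yes | no |
| Marked 'Yes' but never dosed | yes | yes | yes | no |

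Demography is scheduled for everyone at pre-screening and at screening (Protocol Table 7-1). That treated patients also have a Screening Log page is an assumption. It follows naturally from that page carrying the question on whether the subject will enter the study.

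**Step 2: formulas**

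Let T be the number of treated patients and F the number of screen failures in the table, each marked 'No' with a reason.

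- Completed as written = T + F, which is 100 × (T + F)/(T + F) = 100% for any F.
- Discontinued = F, which is 100 × F/(T + F).
- Sum of the two rows = 100% + 100 × F/(T + F), above 100% whenever F is at least 1.
- Completed with a 'Yes' required = T, which is 100 × T/(T + F). The sum is then 100%.

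**Step 3: illustration**

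T = 83, the number enrolled and treated according to the rationale for protocol Amendment 8. F is not given anywhere in the documents, so the values below are assumptions.

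| F (assumed) | Enrolled | Completed as written | Discontinued | Sum as written | Completed with 'Yes' required |
|---|---|---|---|---|---|
| 5 | 88 | 88/88 (100%) | 5.7% | 105.7% | 83/88 (94.3%) |
| 10 | 93 | 93/93 (100%) | 10.8% | 110.8% | 83/93 (89.2%) |
| 20 | 103 | 103/103 (100%) | 19.4% | 119.4% | 83/103 (80.6%) |
| 40 | 123 | 123/123 (100%) | 32.5% | 132.5% | 83/123 (67.5%) |

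The discontinued column is the same before and after the change. Only the completed row moves.

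**The case against.** The strongest reply is that little depends on this row. The discontinued row uses a content-based rule and gives the failure count and percentage correctly wherever a reason is recorded. The reasons are tabulated and every failure is listed. A reader might infer that the table would hide how selective entry was, and that this weakens any generalisation of the response results. The documents do not support that inference, because selectivity can be read from those other outputs.

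A reader might also infer that molecular pre-screening failures are certainly double counted. That is not settled. SAP 2.2 ties enrolment to study informed consent, and SAP 2.3.1 limits its screen failures to patients who signed the study consent form. Patients who signed only the molecular consent may therefore lie outside the table. The protocol glossary, on the other hand, dates enrolment from either consent. The overlap is secure only for main-consent failures.

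It can also be said that a programmer would notice rows adding to more than 100% and use the entry question named in the next bullet. That may happen, but the SAP does not instruct it. Reading completed as meaning that screening ended with any outcome does not help either, since the row would still include patients whom the next row reports as having discontinued during screening.

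All of this limits the scope of the point. The conflict between the two rules remains.

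**Conclusion.** The completed-screening rule is wrong as written. It returns 100% of enrolled patients whatever the number of failures, and it contradicts the row beneath it for every main-consent failure marked 'No' with a reason. This conclusion assumes that the pages are filled as the protocol requires and that the rule is programmed literally. It does not depend on any particular failure count.

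The size in practice is unknown because that count is not in the documents; the figures above only show how the rule behaves. The consequence is minor and confined to one descriptive row. The full analysis, safety, dose-determining and pharmacokinetic sets are all restricted to dosed patients, so the safety, DLT, PK and efficacy results do not change.

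**What to change.** In SAP 2.3.1:

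1. Define completed screening as both pages present and a 'Yes' to the Screening log question on whether the subject will enter the study.
2. Count every 'No' as discontinued, and show any missing reason as 'reason missing'. Adding the 'Yes' condition alone is not enough: the present discontinued rule needs both a 'No' and a reason, so a patient marked 'No' without one would drop out of both rows.
3. Show any patient marked 'Yes' who was never dosed as a screen failure, for example on a line beneath the completed row. Protocol 7.1.1.2 treats anyone who signs the main consent and does not start treatment as a screen failure, whatever the reason.

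The two rows are then mutually exclusive and sum to 100%, provided that the entry question is answered for every enrolled patient. The cost is a line or two of SAP text and a small programming change. The SAP already uses the field in the adjacent row, so no new data are needed.
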